Seven Phase 1 or Phase 1/2 studies in various tumor types (acute lymphocytic leukemia, AML, multiple myeloma, Hodgkin lymphoma/non-Hodgkin lymphoma (HL/NHL), pancreatic, breast, and sarcoma) are ongoing with safety and efficacy data available from more than 130 patients over the various indications. MultiTAA-specific T cells are shown to be clinically safe without cytokine release syndrome (CRS) or neurotoxicity, which are typically associated with chimeric antigen receptor (CAR) T cell therapies. Additionally, since MT-401 is not genetically engineered, there is no risk of insertional mutagenesis. More importantly, despite the lack of lymphodepletion, multiTAA-specific T cell therapy has shown results in patients with more durable responses in lymphoma compared to CAR T cell approaches, and enhancement of response through epitope spreading, thereby preventing antigen-negative or antigen-low tumor escape (Lulla et al, 2019; Carrum et al, 2019; Naik et al, 2018; Lulla et al, 2018; Carrum et al, 2018).

The study rationale is supported by the tolerable safety profile and anti-tumor activity noted in the Baylor Phase 1 dose-escalation study entitled the $\underline{\mathbf{A}}$ dministration of $\underline{\mathbf{D}}$ onor-Derived multi-Tumor-Associated Antigen (multiTAA)- $\underline{\mathbf{SP}}$ ecific T Cells to Patients with $\underline{\mathbf{A}}$ ML or $\underline{\mathbf{m}}$ yelodysplastic syndromes ($\underline{\mathbf{M}}$ DS) (ADSPAM). In addition, the study rationale is supported by the high unmet medical need in AML post-HSCT, where few therapies are available to patients.

Confidential Page 20 of 74

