- Survivin is expressed only at low levels in some normal cell types, such as thymocytes, T cells, basal colonic epithelial cells and CD34⁺ bone marrow-derived stem cells. High Survivin expression has been reported in tumors of lung, breast, colon, stomach, esophagus, pancreas, liver, uterus ovaries, as well as in HL, NHL, leukemias, neuroblastoma, soft-tissue sarcomas, gliomas and melanoma while the normal tissues from these same organs did not express Survivin (Fukuda et al, 2006). Survivin-directed therapies in animal models and a variety of human clinical studies targeting metastatic melanoma, advanced or recurrent urothelial cancer, metastatic renal cell carcinoma, advanced or recurrent breast cancer, prostate cancer, pancreatic cancer, and non-small cell lung cancer using peptides, peptide-loaded dendritic cells, messenger ribonucleic acid (mRNA) vaccines or oncolytic viruses to induce Survivin-specific T cells have revealed no major systemic toxicities (Friedrichs et al, 2006; Saito et al, 2006; Altieri, 2008; Mita et al, 2008; Rapoport et al, 2011).
- In studies at Baylor College of Medicine targeting NY-ESO-1, PRAME, and Survivin expressed in lymphoma, there was no evidence of in vivo toxicities including in individuals with high frequencies of circulating reactive T cells (unpublished results).

Another reported potential risk in patients who receive T cells (Lee et al, 2014a) or bispecific T-cell engagers (Teachey et al, 2013) are serious adverse events (SAEs) associated with CRS. The majority of CRS cases have been reported after the infusion of CAR T cells (Davila et al, 2014; Lee et al, 2014b; Maude et al, 2014a), but CRS can also occur after the infusion of conventional antigen-specific T cells

Confidential Page 24 of 74

(Papadopoulou et al, 2014) or tumor infiltrating lymphocytes (Stevanovic et al, 2015). Several published guidelines for the management of CRS exist (Lee et al, 2014a; Maude et al, 2014b; Neelapu et al, 2018), and includes treatment options based on the clinical severity of the symptoms, such as oxygen, inotropic agents, anti-IL-6 receptor antibody (4-8 mg/kg), anti-tumor necrosis factor-α antibody (5-10 mg/kg), and/or steroids (1-2 mg/kg/day of methylprednisolone or equivalent).

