A minimum of 3 patients each will be treated in Cohorts I and II; if 1 patient experiences a DLT related to MT-401, 3 additional patients will be treated in the cohort (see Section 5.6). If overall, 0 out of 3 patients or 1 out of 6 patients experience a DLT in the specific cohort, this dose will be established as safe for the Phase 2 portion of the study (see Section 5.6). Additional patients may be treated to acquire data such as biomarkers as long as no safety issues arise. In the event that > 1 patient, experiences a DLT (see Section 5.6) related to MT-401, then no further patients will be treated in that cohort. A new cohort of patients will be treated at a lower dose level (DL1) with a flat dose of 25 x 10⁶ cells (Cohorts -I or -II). Dose Level 1 will be repeated with an additional 3-6 patients once new peptides are synthesized for use during manufacturing (Cohort II). If Cohort II is deemed safe for patients, this dose and peptide manufacturer will be used in the Phase 2 portion of the study. In parallel to opening the Phase 2 portion of the study, Cohorts III-V will open to enroll patients using the same standard 3+3 design described above for Cohorts I and II.

Patients who initially receive any dose of MT-401, but are subsequently deemed unevaluable (e.g., important protocol deviation, starting investigational drugs not approved by the Sponsor) and removed from the study will not count as DLTs in the Safety Lead-in and Cohorts III-V and may need to be replaced.

Confidential Page 33 of 74

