5.6. Dose-Limiting Toxicity Determination

A DLT is defined as one of the following AEs reported during the observation period (28 days from the day of the initial MT-401 infusion), if considered to be definitely, probably, or possibly related to MT-

Confidential Page 36 of 74

401 and deemed clinically significant by the investigator; and fulfills any of the following criterion using NCI CTCAE (Version 5.0) with the exceptions as noted below:

- 1. Grade 3-4 GVHD
- 2. Grade 3-4 toxicity felt to be related to, or resulting from CRS
 - Exception: Grade 3 and 4 expected reactions seen with the use of T cell-based immunotherapy, such as (but not limited to) fever and hypotension not requiring pressor support, will not be considered DLTs
- 3. Grade 3-4 infusion reactions that are persistent beyond 72 hours despite optimal medical management
- 4. Any other Grade 3-4 toxicity that is *not* pre-existing and/or *not* due to the underlying malignancy or infection or treatment of disease lasting for extended period of time despite optimal supportive care (for example, nausea, vomiting, and diarrhea lasting > 3 days; fatigue lasting > 7 days)
 - Exception: Laboratory abnormality deemed not to be clinically significant
- 5. Grade 5 toxicity (that is, death)

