7. DISCONTINUATION OF MT-401 AND PARTICIPANT DISCONTINUATION/WITHDRAWAL

7.1. Discontinuation of MT-401

If it becomes necessary for a patient to permanently discontinue MT-401, the patient will remain in the study to be evaluated for safety, response, and survival. See the SoA (Table 1) for data to be collected at the time of intervention discontinuation and follow-up and for any further evaluations that need to be completed.

The following criteria will result in the patient being ineligible for further treatment on the protocol, although safety and response data will continue to be collected as applicable:

- Any patient who develops a DLT. In such patients, the toxicity will be followed until resolution or until their off-study date.
- Any patient who receives any other hematopoietic cell product (e.g., donor leukocyte infusion) except for routine blood product transfusions such as platelets and packed red blood cells. In such patients, AE data collection will cease.
- Any patient who enrolls in another clinical study involving investigational product or other type of medical research judged not to be scientifically/medically compatible with this study or receives antineoplastic treatment for relapse of their primary malignancy within 4 weeks after the T cell infusion. In such patients, adverse event data collection will cease.
- Refusal of the patient to continue treatment or observations.
- Decision by the investigator that discontinuation of treatment is in the patient's best medical interest
- Unrelated medical illness or complication deemed significant by the investigator.

• Death.

Confidential Page 41 of 74

- Progressive Disease.
- Lost to follow-up.
- At the request of Marker Therapeutics, Inc.
- Any patient who becomes pregnant.

Any new clinically relevant finding should be reported as an AE.

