8.3. Adverse Events and Serious Adverse Events

An AE is any untoward medical occurrence in a patient or clinical study patient, temporally associated with the use of MT-401, whether or not considered related to MT-401. An AE can therefore be any unfavorable and unintended sign (including an abnormal laboratory finding), symptom, or disease (new or exacerbated) temporally associated with the use of MT-401. The NCI CTCAE (Version 5.0) for Adverse Events will be utilized for AE reporting. The criteria listed in the Cancer Therapy Evaluation Program (CTEP) NCI Common Toxicity Criteria Scale will be used in grading toxicity, with the exception of CRS toxicity and neurotoxicity that are related to T-cell infusions. CRS toxicity will be graded according to Table 13 (as per Lee et al, 2019 which also contains assessment of neurotoxicity). The CTEP CTCAE is identified and located on the CTEP website at:

http://ctep.cancer.gov/protocolDevelopment/electronic applications/ctc.htm.

AEs will be reported by the patient (or, when appropriate, by a caregiver, surrogate, or the patient's legally authorized representative). In addition, the investigator (or designee) is responsible for detecting, documenting, and recording events that meet the definition of an AE or SAE and remain responsible for following up AEs that are serious, considered related to MT-401 or study procedures, or that caused the patient to discontinue treatment or the study (see Section 7).

If an event is not an AE, then it cannot be an SAE even if serious conditions are met (e.g., hospitalization for signs/symptoms of the disease under study, death due to progression of disease or planned procedures/surgeries).

An SAE is defined as any untoward medical occurrence that, at any dose:

- Results in death
- Is life-threatening (that is, immediate risk of dying)
- Requires inpatient hospitalization or prolongation of existing hospitalization
- Results in persistent or significant disability/incapacity
- Is a congenital anomaly/birth defect
- Is considered significant by the investigator based on appropriate medical judgement

Confidential Page 46 of 74

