11.1.2. Management of Toxicities Related to Cellular Therapy

Based on the mechanism of action of MT-401, AEs of immune related etiology may occur shortly after the first dose or several months after the last dose of treatment. MT-401 must be withheld for drug-related toxicities or severe life-threatening AEs. Use the following references for instructions on management of adverse events, including CRS, neurotoxicity, and immune-related AEs: National Comprehensive Cancer Network (Management of immunotherapy-related toxicities) and Lee et al, 2019.

Confidential Page 62 of 74

Table 13. Grading of Cytokine Release Syndrome Toxicity Events

CRS Parameter	Grade 1	Grade 2	Grade 3	Grade 4
Fever*	Temperature ≥38°C	Temperature ≥38°C	Temperature ≥ 38°C	Temperature ≥38°C
		With		
Hypotension	None	Not requiring vasopressors	Requiring a vasopressor with or without vasopressin	Requiring multiple vasopressors (excluding vasopressin)
	•	And/or [†]		
Нурохіа	None	Requiring low-flow nasal cannula [‡] or blow-by	Requiring high-flow nasal can- nula [‡] , facemask, nonrebreather mask, or Venturi mask	Requiring positive pressure (eg, CPAP, BiPAP, intubation and mechanical ventilation)

Organ toxicities associated with CRS may be graded according to CTCAE v5.0 but they do not influence CRS grading.

Confidential Page 63 of 74

^{*} Fever is defined as temperature ≥38°C not attributable to any other cause. In patients who have CRS then receive antipyretic or anticytokine therapy such as tocilizumab or steroids, fever is no longer required to grade subsequent CRS severity. In this case, CRS grading is driven by hypotension and/or hypoxia.

[†] CRS grade is determined by the more severe event: hypotension or hypoxia not attributable to any other cause. For example, a patient with temperature of 39.5° C, hypotension requiring 1 vasopressor, and hypoxia requiring low-flow nasal cannula is classified as grade 3 CRS.

[‡] Low-flow nasal cannula is defined as oxygen delivered at ≤6 L/minute. Low flow also includes blow-by oxygen delivery, sometimes used in pediatrics. High-flow nasal cannula is defined as oxygen delivered at >6 L/minute.

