 - Exception: Grade 3 and 4 expected reactions seen with the use of T cell-based immunotherapy, such as (but not limited to) fever and hypotension not requiring pressor support, will not be considered DLTs
- 3) Grade 3-4 infusion reactions that are persistent beyond 72 hours despite optimal medical management

- 4) Any other Grade 3-4 toxicity that is **not** pre-existing and/or **not** due to the underlying malignancy or infection or treatment of disease lasting for extended period of time despite optimal supportive care (for example, nausea, vomiting, and diarrhea lasting > 3 days; fatigue lasting > 7 days)
 - Exception: Laboratory abnormality deemed not to be clinically significant
- 5) Grade 5 toxicity (that is, death)

6.4.2.2 *Adverse Events*

An AE is any untoward medical occurrence in a patient or clinical study patient, temporally associated with the use of MT-401, whether or not considered related to MT-401. An AE can therefore be any unfavorable and unintended sign (including an abnormal laboratory finding), symptom, or disease (new or exacerbated) temporally associated with the use of MT-401.

6.4.2.3 *Laboratory Parameters*

Clinical laboratory tests will be collected at the specified time points indicated in the schedule of assessments in Section 1.2.1 of the clinical study protocol. Laboratory tests to be collected (on days of MT-401 administration, labs should be performed prior to MT-401 administration) include hematology, serum chemistry, and coagulation tests.

6.4.2.4 *Vital Signs*

Vital signs will be performed at the specified time points indicated in the schedule of assessments in Section 1.2.1 of the clinical study protocol. Temperature, pulse rate, and blood pressure will be assessed, and if clinically indicated, respiratory rate will also be assessed.

6.4.2.5 *Physical Examination*

Physical examinations will be performed at the specified time points indicated in the schedule of assessments in Section 1.2.1 of the clinical study protocol. A complete physical examination will be performed as per institutional guidelines at baseline and will include, at a minimum, assessments of the Cardiovascular, Respiratory, Gastrointestinal and Neurological systems, and height (at Screening) and weight will also be measured and recorded. A brief physical examination will include, at a minimum, assessments of the Cardiovascular, Respiratory, and Gastrointestinal systems.

6.4.2.6 *GVHD Assessments*

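### The exception to the CRS dose-limiting toxicity criterion is an open list with no limit on hypoxia, so some Grade 3-4 CRS could stay out of the 3+3 count

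*Protocol*

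**What the plan says.** Protocol 5.6 defines a DLT as an AE within 28 days of the first infusion that is definitely, probably or possibly related to MT-401, is judged clinically significant by the investigator, and meets one of five criteria. Criterion 2 is Grade 3-4 toxicity attributed to CRS. Its exception begins "Exception: Grade 3 and 4 expected reactions seen with the use of T cell-based immunotherapy, such as (but not limited to) fever and hypotension" and continues with the condition that the hypotension needs no pressor support. SAP 6.4.2.1 carries the same exception ("Exception: Grade 3 and 4 expected reactions seen with the use of T cell-based immunotherapy") and adds no definition of expected.

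Two rules depend on the resulting count. Protocol 4.5 sets the clearing rule: "0 out of 3 patients or 1 out of 6 patients experience a DLT in the specific cohort, this dose will be established as safe". One DLT in the first three patients adds three more, and more than one stops the cohort. Under 7.1, "Any patient who develops a DLT" is ineligible for further treatment.

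The grading scale is given in two ways. The opening of 5.6 names CTCAE v5.0, whereas 8.3 says "CRS toxicity will be graded according to Table 13". In Table 13, Grade 3 can be reached through hypotension needing a vasopressor or through hypoxia needing high-flow cannula, "facemask, nonrebreather mask, or Venturi mask". Grade 4 hypoxia is the need for positive pressure.

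**The concern.** The exception asks what is expected with T cell-based immunotherapy as a class. Protocol 2.2.5 says that "CRS can also occur after the infusion of conventional antigen-specific T cells". A literal reader could therefore place CRS itself among the class reactions, and the exception would remove events that criterion 2 exists to count. The pressor condition closes that route for hypotension. It says nothing about hypoxia or other CRS toxicity.

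What is at stake is whether such an event enters the formal 3+3 count, and whether the patient is automatically barred from the remaining infusions. Doses are planned at Weeks 0, 2 and 4, so CRS after the first dose bears directly on the second and third. Two sites could classify the same event differently and both be within the text.

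**Working it through.** **Step 1: the named examples on each scale.** On Table 13, fever alone is Grade 1 and hypotension without a vasopressor is Grade 2. If Table 13 governs, the two examples remove no Grade 3-4 CRS, and the exception can act only through reactions it does not name. If CTCAE governs, 5.6 departs from 8.3. Either way the boundary is not stated.

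**Step 2: a case the text does not settle.** Take fever with hypoxia needing a facemask (Table 13 Grade 3), possibly related, clinically significant, on day 5, resolved within 72 hours.
- Criterion 3 needs an infusion reaction lasting beyond 72 hours, so it does not apply.
- Criterion 4 needs an extended duration, so it does not clearly apply.
- Criterion 2 applies unless the event is excepted as expected.

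Counted, the cohort stands at 1/3 and expands to six. Excepted, it stands at 0/3 and clears. By the same logic a cohort at 2/6 (stop) becomes 1/6 (clear).

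**Step 3: effect on the clearing probability.** The plan gives no operating characteristics for the 3+3, so there is no figure to reproduce. With q the per-patient probability of a counted DLT, the rule in 4.5 gives

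P(clear) = (1 − q)³ + 3q(1 − q)²(1 − q)³ = (1 − q)³ + 3q(1 − q)⁵.

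Let d be the rate of other DLTs and c the rate of Grade 3-4 CRS open to exception, independent of each other. If all such CRS is counted, q = 1 − (1 − d)(1 − c). If all is excepted, q = d. Both d and c are assumptions, because the documents supply neither.

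For d = 0.10 and c = 0.023:
- counted: q = 1 − 0.9 × 0.977 = 0.1207, and P(clear) = 0.8793³ + 3 × 0.1207 × 0.8793⁵ = 0.680 + 0.190 = 0.870;
- excepted: P(clear) = 0.9³ + 3 × 0.1 × 0.9⁵ = 0.729 + 0.177 = 0.906.

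The difference is 3.6 percentage points. Over a range of assumptions:

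| Other DLTs (d) | Grade 3-4 CRS (c) | P(clear), all counted | P(clear), all excepted |
|---|---|---|---|
| 0% | 2.3% | 0.994 | 1.000 |
| 0% | 10% | 0.906 | 1.000 |
| 0% | 20% | 0.709 | 1.000 |
| 10% | 2.3% | 0.870 | 0.906 |
| 10% | 10% | 0.730 | 0.906 |
| 10% | 20% | 0.536 | 0.906 |

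Excepting only some of the events gives values between the two columns.

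**Step 4: cost in patients of counting every event.** A cohort expands when exactly one of the first three patients has a DLT. For d = 0.10 and c = 0.023 this has probability 3 × 0.1207 × 0.8793² = 0.280, against 3 × 0.1 × 0.9² = 0.243 if the CRS is excepted. The extra enrolment is 3 × (0.280 − 0.243) = 0.11 patients per cohort on average.

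**The case against.** Read with its examples, the exception is aimed at mild, familiar reactions, and facemask hypoxia is not of that kind. Protocol 2.1 also reports that "MultiTAA-specific T cells are shown to be clinically safe without cytokine release syndrome (CRS) or neurotoxicity", which makes severe CRS hard to call expected for this product. Both points have force as to intent. They do not close the text, because the list is expressly open and its test is the therapy class, not MT-401.

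Three stronger readings are tempting, and the documents do not support them.
- A reader might infer that any Table 13 Grade 3-4 CRS can be excepted. The pressor condition keeps pressor-requiring hypotension in the count, and a Grade 5 event is a DLT under criterion 5.
- A reader might infer that nobody judges the event and that expected has no anchor anywhere. The investigator makes the clinical-significance call, and the Sponsor review committee (9.4) reviews the toxicities of the Safety Lead-in and meets again after Cohort III and after Cohorts IV-V. Section 2.3 points to the Investigator's Brochure for expected AEs of MT-401, although 5.6 does not cite it.
- A reader might infer that an excepted event leaves the next infusion unguarded. Section 11.1.2 requires MT-401 to be withheld for drug-related toxicity, 8.3.1 requires any-grade CRS to be reported within 24 hours, section 8 sends safety concerns to the Sponsor at once, 7.1 lets the investigator or Sponsor stop treatment, and 9.3.1 bases the dose decision on all safety data as well as the DLT count.

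What survives is narrower. None of these safeguards puts the event into the 3+3 count or makes the stop automatic, and 6.6 allows infusions to resume after a toxicity delay without a CRS-specific criterion.

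**Conclusion.** The concern holds for hypoxia-driven and other Grade 3-4 CRS that falls outside the pressor condition. As written, such an event may or may not be a DLT, and the text does not say which. This is a drafting weakness in a safety rule with several other layers of protection. It is worth correcting, but it does not invalidate the dose-finding part.

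At the level of the rule, one excepted event can change a cohort's outcome. In probability, the size depends on rates that the documents do not give. The 3.6-point difference rests on the assumed 10% and 2.3%, on independence, and on every such event being excepted.

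A reader might take section 2.1 as zero CRS in 130 patients, derive a one-sided 95% upper bound of 1 − 0.05^(1/130) = 2.3%, and conclude that the effect is at most 0.6 points (1.000 − 0.994). That does not follow. Section 2.1 makes a general statement about a programme of more than 130 patients across tumour types, without a count of 0/130 and without doses. Section 4.3.2 reports only two evaluated patients at the equivalent of 100 x 10⁶ cells and one at 200 x 10⁶. The documents do not say whether earlier patients had the accelerated product. The 0.6 figure also assumes that no other DLT can occur. No upper bound can be stated.

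**What to change.** In Protocol 5.6 criterion 2 and SAP 6.4.2.1:
- Limit the exception to fever, and to hypotension that needs no pressor support, and delete the open-ended wording and the word expected.
- State that CRS is graded by Table 13, and that Grade 3-4 CRS meeting the relatedness, clinical-significance and 28-day conditions is a DLT and may not be excepted as expected.
- State that organ toxicities accompanying CRS are graded by CTCAE v5.0, in line with the note to Table 13.
- In the SAP, adopt the protocol's three-level relatedness wording and name Cohorts I-V, since SAP 6.4.2.1 now says only related and refers only to the Safety Lead-in period.

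The 7.1 stop then applies to these events, so they need no separate rule for resuming. The count will still rest on the investigator's clinical-significance judgement, which this change leaves in place. Once Table 13 governs, the closed exception has little left to remove beyond signs graded by CTCAE.

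The cost is an amendment with IRB/IEC approval before implementation (10.1), a matching SAP edit, no new data, and occasional expansion of a cohort from 3 to 6 patients. The definition would also differ from the one applied to cohorts already cleared, so the report should state which definition each cohort used.
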